10.8 Sample Size Justification

10.9 Analyses to be Conducted

Analyses described below will be performed on all enrolled and ablated subjects.

Disposition of Study Subjects

Subject disposition will be summarized using counts and percentages. The number and percentage of subjects completed and discontinued along with the specific reasons for discontinuation will be tabulated by ablation group and in total.

Demographic and Baseline Characteristics

Summary statistics will be provided for subject demographics and pre-operative ablation characteristics.

Primary and Secondary Endpoint Analyses

The number and percentage of tumors achieving Technique Efficacy will be summarized and a 95% confidence interval will be estimated. Hypothesis testing for the primary endpoint will be performed using the methodology described in the previous section. The number and percentage of tumors achieving Technical Success will also be summarized, and a 95% confidence interval will be estimated. Local Tumor Progression will be summarized in a similar manner. Only target lesions will be included in the primary endpoint analysis for Technique Efficacy and primary summaries of Technical Success and local Tumor Progression. Data collected on non-target tumors for these endpoints will be summarized separately and not included as part of the primary analysis. The analysis of target tumors for these three endpoints will also include a subject level summary that will be secondary or supportive to the tumor level analysis.

Summary statistics will be provided for other secondary endpoints, as appropriate, for continuous or categorical variables. Local Tumor Progression Free Survival, Progression Free Survival, and Overall Survival will be estimated using the Kaplan-Meier method and confidence intervals will be provided.

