## 1 Study Design

This is a prospective, multicenter, single-arm study of transbronchial microwave ablation using robotic-assisted bronchoscopy in adult subjects with oligometastatic tumors ( $\leq 2\text{cm}$ ) in the lung, located in the outer two-thirds and not closer than 1cm to the pleura (including fissures), with colorectal, renal, or sarcoma histology.

Subjects with at least one oligometastatic tumor in the lung who meet all inclusion/exclusion criteria will have transbronchial microwave ablation performed using CBCT scan for probe guidance and confirmation. Subjects will be followed for 12 months following the first ablation procedure for safety and effectiveness outcomes.

Overall, the study will include up to 145 subjects across approximately 15 sites, where principal investigators will be licensed pulmonologists/interventional pulmonologists or thoracic surgeons who have completed at least 20 diagnostic cases using the MONARCH Platform including at least 5 cases using CBCT and completed the Sponsor-required FLEX MC training.

In this study, “target” tumors are defined as lung tumors that are treated with FLEX MC at the index ablation procedure (i.e., Visit 2). A subject may have a maximum of two target tumors. “Non-target” tumors are defined as lung tumors that are treated with FLEX MC during study follow-up after completion of the primary endpoint, Technique Efficacy assessments at Visit 3 (i.e., Visits 3-6). A subject may not have more than three total tumors treated with FLEX MC (including target and non-target tumors).

A central review committee of radiologists will independently review all CT scans (and other scans, as applicable) taken throughout the clinical study in an effort to standardize scan assessment and to minimize potential bias of the treating physician. Both the clinical site’s radiographic assessment and the central review committee’s assessment will be captured within the CRFs and reported within the final Clinical Study Report. The central review committee assessment for the following key endpoints will be used for the final analysis.

Assessment	Visit 1 (Screening)	Visit 2 (Ablation Visit)	Visit 3 (30 days post-ablation)	Visit 4 (3 months post-ablation)	Visit 5 (6 months post-ablation)	Visit 6 (12 months post-ablation)
Tumor size* (smallest and largest diameters)	X					
Ablation zone (smallest and largest diameters)		X				
Smallest minimal ablation margin		X				
Technical Success		X				

Technique Efficacy			X			

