## **5 Levels of Significance**

The following hypotheses will be evaluated in this study:

$$H_0: p \leq 0.80 \text{ vs.}$$

$$H_1: p > 0.8$$

where  $p$  represents the true 30-day Technique Efficacy rate of FLEX MC and 0.80 is the performance goal, which was determined through an internal systematic literature review and meta-analysis of microwave and radiofrequency ablation systems used in the treatment of lung tumors.

A one-sided significance level of 0.025 will be used to test the hypotheses above. If the lower bound of the confidence interval is above 0.8, then the following secondary endpoints will be provided with 95% confidence intervals at month 12, in addition to the descriptive statistics:

- Local Tumor Progression Free Survival,
- Progression Free Survival,
- Disease Specific Survival, and
- Overall Survival

No other formal hypothesis tests are planned for this study and estimation for all other endpoints will be provided descriptively.

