## 7 Sample Size Justification

Establishment of the performance goal for Technique Efficacy was determined through performing a systematic literature review and meta-analysis to obtain a pooled estimate for MWA and RFA based on available published literature. Ovid MEDLINE®, Embase, and Evidence Based Medicine Reviews from January 1, 2005 to March 31, 2021 were searched to identify literature reporting on studies that included at least 20 adult subjects with NSCLC or lung metastases who were treated with MWA or RFA and reported on Technique Efficacy at a target of one-month post-ablation (up to a maximum of 3 months). Study designs included randomized controlled trials, comparative observational studies, and single-arm studies. Conference abstracts, studies with less than 20 subjects, and studies assessing salvage therapies were excluded.

A total of 19 studies of percutaneous ablation were included with random-effects and fixed-effects methodologies being applied to obtain a point estimate of average Technique Efficacy and corresponding 95% confidence interval.

Results from the representative set of MWA studies demonstrated a point estimate of average Technique Efficacy to be 89% with 95% confidence interval (81%, 94%). In consideration of the lower bound of the estimated confidence and a clinically meaningful minimum acceptable level of performance while recognizing that there may be some learning curve with the new technology and allowing for a modest region of indifference, a performance goal of 80% was established for this study.

Determination of the study sample size was then performed based on a power analysis where the null hypothesis being considered was  $H_0: p \leq 0.80$  against the alternative hypothesis of  $H_1: p > 0.80$ , where  $p$  represents the true 30-day Technique Efficacy rate of FLEX MC and 0.80 is the performance goal. It is assumed that the expected Technique Efficacy rate observed for FLEX MC will be 0.90 and, therefore, a sample size of 137 subjects will provide greater than 90% power for evaluating the above hypotheses at a one-sided significance level of 0.025 using the Normal approximation to the Binomial distribution. Accounting for up to 5% dropout at the 30-day timepoint leads to a sample size of 145 subjects. This conservatively assumes one target tumor per subject.

At least 50% of the study population will be enrolled from sites in the United States.

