## 8.8 Primary and Secondary Endpoint(s) and Associated Hypotheses

### 8.8.1 Primary Endpoint(s) and associated hypotheses

Technique Efficacy is defined as the proportion of subjects with ablation of the target tumor(s) with the ablation zone completely overlapping or encompassing the entire target tumor(s) using CT imaging at 30 days (-7 to +14 days) post the original ablation procedure. If >1 target tumor, both tumors have to meet TE in order to consider TE for the subject.

The number and percentage of tumors achieving Technique Efficacy will be summarized and a 95% confidence interval will be estimated with the Wilson score confidence intervals as shown below. Hypothesis testing for the primary endpoint will be performed using the methodology described in the Section 5.

$$\left( \frac{\hat{p} + \frac{z_{\alpha/2}^2}{2n} - z_{\alpha/2} \sqrt{\frac{\hat{p}}{n} + \frac{z_{\alpha/2}^2}{4n^2}}}{1 + \frac{z_{\alpha/2}^2}{n}}, \frac{\hat{p} + \frac{z_{\alpha/2}^2}{2n} + z_{\alpha/2} \sqrt{\frac{\hat{p}}{n} + \frac{z_{\alpha/2}^2}{4n^2}}}{1 + \frac{z_{\alpha/2}^2}{n}} \right)$$

Technique Efficacy (TE) at Visit 3 (30 days post-ablation) will be performed on observed data only and involving only target lesions. The TE rate is the number of subjects achieving TE divided by the number of subjects completing Visit 3.

To assess the robustness of the conclusion based on observed data for the primary endpoint, sensitivity analyses imputing missing data is proposed as the following:

1. Worst-case analysis: All subjects not completing Visit 3 will be assumed to have not achieved TE.
2. Best-case analysis: All subjects not completing Visit 3 will be assumed to have achieved TE.
3. Tipping point analysis: All missing data will be imputed with either having achieved TE or not achieved TE, i.e., the denominator of the TE rate is based on the analysis set. By adding one TE event at each time, the p-value is calculated (worst-case to best-case). The tipping point is when the p-value is changed from ( $\geq 0.05$  to  $< 0.05$ ). After such a tipping point is determined, clinical judgment can be applied as to the plausibility of the assumptions underlying this tipping point (essentially, if we have 145 ITT patients, tipping point is 126 TE events; if we have 130 ITT patients, tipping point is 113 TE events).

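### The tumor-level Technique Efficacy interval makes no allowance for two tumors in one subject, and is too narrow when two-tumor subjects are present and their outcomes correlate positively

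*SAP*

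**What the plan says.** SAP 8.8.1 plans a tumor-level result for the primary endpoint: "percentage of tumors achieving Technique Efficacy will be summarized and a 95% confidence interval will be estimated with the Wilson score confidence intervals". SAP 1 says "A subject may have a maximum of two target tumors". Target tumors are those treated at the index procedure, and Protocol 5.3 (Note 1) limits one session to two tumors on the same side. Two targets in one subject are therefore treated in the same lung on the same day.

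SAP 8.8.1 also defines Technique Efficacy by subject. Both tumors must succeed, the rate is subjects succeeding over subjects completing Visit 3, and the tipping points count patients. Protocol 10.9 differs: it puts the tumor level first and calls the subject-level summary secondary or supportive.

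On the other two imaging endpoints the documents also differ. Protocol 10.9 says "The number and percentage of tumors achieving Technical Success will also be summarized, and a 95% confidence interval will be estimated" and treats Local Tumor Progression likewise, without naming a method. SAP 8.8.2 plans only counts and percentages for both, and SAP 5 makes endpoints outside its short list of survival measures descriptive.

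Neither document mentions clustering, a robust variance or any other within-subject adjustment.

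**The concern.** A Wilson interval takes its variance from a count of independent yes/no results. Two tumors ablated in one subject, in one session, by one operator share much that could make them succeed or fail together. If they do, the tumor count overstates the information and the interval is too short.

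This question is separate from which unit is primary. Naming the subject as the primary unit would leave the tumor-level interval planned and unadjusted. What depends on the unit is the consequence. With the subject as the unit, the stake is the stated precision of a supporting result. With the tumor as the unit, it is the error rate of the test against the performance goal.

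**Working it through.** **Inputs from the documents.** SAP 5: "A one-sided significance level of 0.025 will be used to test the hypotheses above", and "0.80 is the performance goal, which was determined through an internal systematic literature review and meta-analysis". SAP 7: "It is assumed that the expected Technique Efficacy rate observed for FLEX MC will be 0.90", "a sample size of 137 subjects will provide greater than 90% power for evaluating the above hypotheses", and the test is planned "using the Normal approximation to the Binomial distribution". There are at most two target tumors per subject (SAP 1).

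**Assumed inputs.** The documents do not give the share of subjects with two targets (f) or the within-subject correlation (r). I take f = 0.2-0.4 and r = 0.2-0.5 as the main range, and also show f = 0.1.

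**1. Reproduce the plan's own figures.**
- n = [(1.960·√(0.80·0.20) + 1.282·√(0.90·0.10)) / 0.10]² = 136.5, rounded up to 137. Power at 137 is 90.1%.
- 137/0.95 = 144.2, rounded up to 145.
- The smallest count whose standard Wilson lower limit exceeds 0.80 is 126 of 145 and 113 of 130. Both match the SAP's tipping points, which count patients.
- The Wilson formula as it reads in the available text lacks the factor (1 − p) under the root. That may be a reading error. The tipping points fit the standard formula, so I use that.

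**2. Design effect.** With cluster sizes of 1 or 2, design effect = 1 + r·(Σm²/Σm − 1) = 1 + r·2f/(1+f).
- f = 0.2, r = 0.2: 1 + 0.2·0.333 = 1.07, square root 1.03.
- f = 0.3, r = 0.2: 1.09, square root 1.05.
- f = 0.3, r = 0.5: 1.23, square root 1.11.
- f = 0.4, r = 0.5: 1 + 0.5·0.571 = 1.29, square root 1.13.

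The correct standard error is thus 3-13% larger than the plain one. If f = 0 or r = 0, nothing changes.

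**3. Effect on the interval at the planned rate.** At 0.90 with f = 0.3 (about 178 tumors), the plain 95% Wilson interval is 84.7-93.6%. With the sample size divided by the design effect it is 84.4-93.7% at r = 0.2 and 84.0-93.9% at r = 0.5.

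**4. Effect on the test, if the tumor-level bound were used.** I simulated trials of 137 subjects at a true tumor-level rate of 0.80, counting a pass when the plain Wilson lower limit exceeds 0.80. One-sided size:

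| Two-tumor share (tumors) | r = 0 | r = 0.2 | r = 0.3 | r = 0.5 |
|---|---|---|---|---|
| 10% (151) | 0.020 | 0.022 | 0.023 | 0.025 |
| 20% (164) | 0.019 | 0.022 | 0.023 | 0.027 |
| 30% (178) | 0.025 | 0.031 | 0.034 | 0.039-0.040 |
| 40% (192) | 0.021 | 0.027 | 0.031 | 0.037 |

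The column r = 0 varies because the pass mark is a whole number of tumors. At 10-20% that leaves slack below 0.025, and clustering mostly uses it up.

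**5. A borderline case.** With 178 tumors, 153 successes give a plain lower limit of 0.801, a pass. With f = 0.3 and r = 0.3 the design effect is 1.14 and the limit is 0.796, a fail. At 154 successes the adjusted limit is 0.803 and passes again, so the disagreement spans one tumor.

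**The case against.** The strongest reply is that the SAP's primary endpoint is a subject-level rate. One yes/no result per subject has no within-subject correlation, and the tipping points confirm that the SAP's authors were counting patients. On that reading the tumor-level interval is descriptive, and subject-level summaries of all three imaging endpoints are already planned beside the tumor-level ones. This stands for the SAP's rate. It does not remove the point, because the tumor-level interval is still planned, and Protocol 10.9 still ranks the tumor level above the subject level.

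A second reply is that the effect is small and rests on assumed inputs. This also stands. Clusters of at most two limit the design effect, and at 10-20% two-tumor subjects the size hardly moves from nominal. The 30% row of the table looks worse than the 40% row partly because its pass mark leaves no slack even under independence.

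A third reply concerns scope. A reader might infer that the SAP's intervals for Technical Success and Local Tumor Progression are too narrow as well. The documents do not support that: SAP 8.8.2 plans no such intervals, and Protocol 10.9 names no method that could be called wrong.

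**Conclusion.** The point holds as a conditional and modest one. The interval method in SAP 8.8.1 is not right for tumor percentages when subjects can contribute two tumors. It gives too narrow an interval if some do and their outcomes correlate positively. Under the assumed ranges the standard error should be 3-13% larger.

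A reader might go further and infer that the primary test is anti-conservative. The documents do not establish this. SAP 5 refers to the lower bound of the confidence interval without saying which, while SAP 8.8.1 defines the rate by subject and attaches the interval to tumors. Only if the tumor-level bound decides would the size pass 0.025. It would then be about 0.027-0.040 with 30-40% two-tumor subjects and a correlation of 0.2-0.5, and 0.022-0.027 with 10-20%.

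For Technical Success and Local Tumor Progression the finding is a mismatch between documents: Protocol 10.9 plans tumor-level intervals and SAP 8.8.2 does not. The same caution applies to any interval that is kept.

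**What to change.** - In SAP 8.8.1, compute the tumor-level Technique Efficacy interval with the subject as the cluster. Use either a Wilson interval on the effective sample size (tumors divided by the estimated design effect) or GEE with an independence working correlation and robust variance. Name the choice in advance.
- State in SAP 5 which interval is compared with 0.80, and align this with Protocol 10.9.
- Reconcile SAP 5 and 8.8.2 with Protocol 10.6 and 10.9 on whether Technical Success and Local Tumor Progression get intervals. Use the clustered method for any tumor-level interval that is kept.
- Keep the ordinary Wilson interval for subject-level rates.

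The cost is a few sentences in the SAP, a few lines of code and slightly wider tumor-level intervals. The change should be in place before the interim analysis after all subjects complete Visit 3, because that analysis evaluates the performance goal.

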#### 8.8.2 Secondary Endpoints and associated hypotheses

##### **Technical Success and Local Tumor Progression:**

Technical Success is defined as: All A0 and A1 ablation classification determinations (complete tumor ablation with a surrounding minimal margin) as assessed by cone beam CT (CBCT) imaging, immediately following the ablation procedure. (Note: A0 = Complete tumor ablation with an ideal minimal margin, i.e., a surrounding minimal margin of at least 5mm. A1 = Complete tumor ablation with a minimal margin, i.e., a surrounding minimal margin of less than 5mm but more than 0mm.)

Local Tumor Progression (LTP) is defined as: Recurrence of originally ablated target tumor(s) within or abutting the ablation zone using 30-day post-ablation imaging as the baseline.

The number and percentage of target tumors achieving Technical Success will be summarized. Local Tumor Progression (target tumors only) will be summarized in a similar manner.

Data collected on non-target tumors for these endpoints will be summarized separately. In addition, Technique Efficacy, Technical Success, and Local Tumor Progression results will be include a subject level summary in addition to the tumor level analysis.

Detail regarding new or recurrent lung tumors post procedure will be summarized similarly to the pre-ablation, such as target/non-target, location, size, and distance from pleura.

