4.3 Secondary Endpoints

- Technical Success: All A0 and A1 ablation classification determinations (complete tumor ablation with a surrounding minimal margin) as assessed by cone beam CT imaging, immediately following the ablation procedure.
- Navigational Success: Successful navigation to the targeted peripheral lung tumor(s) as confirmed using cone beam CT (CBCT).
- Local Tumor Progression (LTP): Recurrence of originally ablated target tumor(s) within or abutting the ablation zone using 30-day post-ablation imaging as the baseline. Measuring progression details will be outlined in a separate Imaging Charter.
- Local Tumor Progression Free Survival (LTPFS): Time from the ablation until local tumor(s) progression (LTP) or death, whichever occurs first. Measuring progression details will be outlined in a separate Imaging Charter.

- Progression Free Survival: Time from the original ablation until tumor(s) progression or death, whichever occurs first (includes local, regional, or distant progression). Measuring progression details will be outlined in a separate Imaging Charter.
- Disease (cancer) Specific Survival: Time from the original ablation until death from the treated primary malignancy.
- Overall Survival: Time from the original ablation until subject death (includes death from any cause).
- Repeat Ablation Efficacy Rate: Rate of original tumors that have been re-ablated successfully (i.e., Technical Success of tumors that have been re-ablated/all original tumors that have been re-ablated).
- Change in all available PFTs (pulmonary function tests) from pre-ablation baseline values to values at 3 months, 6 months, and 12 months post-ablation.
- Change in overall health-related quality of life (HRQOL) and sub-scales, including physical functioning and pain domains, per the validated EORTC QLQ-C30 and QLQ-LC13 questionnaires throughout the duration of the study.

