If target tumors recur after the original ablation, they may be re-ablated after the Visit 3 assessment for Technique Efficacy has been completed. A re-ablation will not change or extend the follow-up schedule. Additionally, no single tumor should be ablated more than twice during the 12-month follow-up period (i.e., the original ablation procedure and a re-ablation procedure at a separate visit). **Robotic Navigation Portion of Procedure**

Cone beam CT will be used in all cases to confirm the presence of the tumor(s) immediately before initiating the procedure. Navigation to the target tumor(s) will be performed using the MONARCH Platform. The MONARCH Platform is a novel robotic-assisted, software driven, endoscope articulation system which can electromechanically insert, steer, and withdraw a flexible endoscope to patient airways under continuous, real-time, direct, visual control by a physician operator.

Users must follow all instructions for use supplied with the MONARCH Platform, its components, instruments, and accessories, including any instructions for use (IFUs) provided with instruments or accessories. The provided IFU is the primary source for detailed safety information. The MONARCH Platform and its accessories are intended to provide bronchoscopic visualization of and access to patient airways for diagnostic and therapeutic procedures.

Microwave Ablation Portion of Procedure

The ablation will be performed using the NEUWAVE FLEX MC Microwave Ablation System, per the device's User Manual and Instructions for Use (IFU), and the performing physician's clinical judgment.

All ablations will be performed under general anesthesia via a transbronchial approach. Prophylactic antibiotics should be administered pre-ablation per site SOC.

The size of the tumor(s) will be measured and recorded on the day of ablation (Visit 2). Afterwards, the Monarch Platform will be used to navigate the microwave ablation probe to the target tumor and CBCT will be used to confirm probe position/placement.

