**Time to Event Endpoints:**

Local Tumor Progression Free Survival (LTPFS) is defined as: Time from the ablation until local tumor(s) progression (LTP) or death, whichever occurs first.

Progression Free Survival (PFS) is defined as: Time from the original ablation until tumor(s) progression or death, whichever occurs first (includes local, regional, or distant progression). Specifically: For local tumors, time from the original ablation until tumor(s) progression or death, whichever occurs first. For regional and distant tumors, time from study day 0 or last local therapy (if treated after study initiation) until tumor(s) progression or death, whichever occurs first.

Disease (cancer) Specific Survival (DSS) is defined as: Time from the original ablation until death from the treated primary malignancy.

Overall Survival (OS) is defined as: Time from the original ablation until subject death (includes death from any cause).

Local Tumor Progression Free Survival (LTPFS), Progression Free Survival (PFS), Disease Specific Survival (DSS), and Overall Survival (OS) will be estimated using the Kaplan-Meier method with 95% confidence intervals provided at month 12. The time from the day of the initiation ablation procedure to the specific event will be derived.

Patients who are re-ablated are considered as reaching an event respectively for each of the LTP, LTPFS and PFS event definitions.

Patients without a progression event, as defined above, will be censored by the last contact date (the last date in the study).

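### A target tumor that fails Technique Efficacy at 30 days can still count as free of local progression, because LTP is judged against the 30-day scan in all target tumors; this can lower reported LTP and raise 12-month LTPFS.

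*SAP*

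**What the plan says.** SAP 8.8.2 and Protocol 4.3 both define LTP as "Recurrence of originally ablated target tumor(s) within or abutting the ablation zone using 30-day post-ablation imaging as the baseline". On the analysis, the SAP says "Local Tumor Progression (target tumors only) will be summarized in a similar manner", meaning as a number and percentage of target tumors. Neither document restricts this to tumors that met TE at Visit 3.

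LTPFS is "Time from the ablation until local tumor(s) progression (LTP) or death, whichever occurs first". The SAP then adds two rules. On re-ablation: "Patients who are re-ablated are considered as reaching an event respectively for each of the LTP, LTPFS and PFS event definitions". On censoring: "Patients without a progression event, as defined above, will be censored by the last contact date (the last date in the study").

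The central review tables in Protocol 4.5 and SAP Section 1 schedule the TE reading at Visit 3 only and the local progression reading at Visits 4, 5 and 6 only. On re-ablation, Protocol 6.1 says "If target tumors recur after the original ablation, they may be re-ablated after the Visit 3 assessment for Technique Efficacy has been completed". Protocol 4.3 adds, for LTP, LTPFS and PFS, "Measuring progression details will be outlined in a separate Imaging Charter". That charter is not among the documents reviewed.

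**The concern.** A target tumor that the ablation zone does not fully cover at Visit 3 has already failed locally under the trial's own primary endpoint. For LTP, however, the Visit 3 scan is the reference, so residual disease on it is the starting point and not an event. The tumor becomes an LTP event only if it is later read as progressing beyond that scan or if the patient is re-ablated. A residual tumor that stays stable, or that is treated by something other than re-ablation (Protocol 5.5 allows other local and systemic treatment once the restriction period is over), stays out of the LTP count. Its subject is censored at last contact in LTPFS.

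Two consequences follow. First, two subjects with the same residual tumor can be scored differently because of the treatment chosen afterwards. Second, the LTP percentage mixes persistence with recurrence. LTPFS is one of four endpoints that SAP Section 5 gives a 12-month confidence interval if the primary endpoint is met, so its estimate will be read as evidence on durability. The second interim analysis reports TE after all subjects complete Visit 3, before the 12-month analysis. A rule for known failures is best fixed before those results are seen.

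**Working it through.** **Inputs from the documents.** On the planned TE rate, SAP Section 7 says "It is assumed that the expected Technique Efficacy rate observed for FLEX MC will be 0.90". The performance goal is 0.80, tested at one-sided 0.025. The planned size is 137 evaluable and 145 in total after 5% dropout. The microwave literature estimate of TE is 89% (81% to 94%). SAP 8.8.1 gives 126 TE successes as the tipping point for 145 subjects.

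**The plan's own figure.** n = [(1.96 × √(0.8 × 0.2) + 1.282 × √(0.9 × 0.1)) / 0.10]² = 136.5, rounded up to 137; power at 137 is 90.1%. Then 137 / 0.95 rounds up to 145. Both figures reproduce. An exact binomial check at n = 145 also gives 126 as the smallest passing count (one-sided alpha 0.0204). The documents state no planning figure for LTP or LTPFS.

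**Number of TE failures**, with one target tumor per subject as in SAP Section 7:
- TE 90%: 0.10 × 137 = 13.7, or 0.10 × 145 = 14.5.
- 126/145: 145 − 126 = 19, which is 13.1%.

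**LTPFS at 12 months.** Let S be LTPFS among TE successes, g the share of TE failures that become events by progression reading or re-ablation, and 0.95 the share of the remaining failures still alive. S, g and the 5% deaths are assumptions; censoring is ignored.
- As written: TE × S + (1 − TE) × (1 − g) × 0.95
- With failures counted as events: TE × S
- Difference: (1 − TE) × (1 − g) × 0.95, so S cancels.

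At TE = 0.90 and, for illustration, S = 0.85, counting failures gives 0.90 × 0.85 = 76.5%.

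| g | LTPFS as written | Overstatement |
|---|---|---|
| 0 | 76.5% + 9.5% = 86.0% | 9.5 points |
| 0.5 | 76.5% + 4.75% = 81.25% | 4.75 points |
| 1 | 76.5% | 0 |

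At 126/145 the maximum, at g = 0, is 0.131 × 0.95 = 12.4 points.

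**LTP rate.** Let f be the share of TE failures and L the LTP rate among TE successes. L = 15% is assumed, suggested by the local control above 85% that Protocol 3.0 quotes for percutaneous ablation. Death and censoring are ignored.
- As written: (1 − f) × L + f × g
- With every failure an event: (1 − f) × L + f
- Understatement: f × (1 − g)

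At f = 10%, LTP as written is 13.5%, 18.5% or 23.5% for g = 0, 0.5 or 1. It is 23.5% if every failure is an event and 15.0% among TE successes alone. At g = 0 the failures make the overall LTP rate better than the rate among successful ablations. With f from 6% (the upper literature limit of 94%) to 20% (the performance goal), the largest understatement runs from 6 to 20 points; at g = 1 it is zero throughout.

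**The case against.** A reader might infer that every TE failure is scored as locally controlled. The documents do not support that. Any re-ablated patient is an LTP, LTPFS and PFS event, and the protocol opens re-ablation once the Visit 3 assessment is done. Chest CT with central reading follows at Visits 4 to 6, so growth can be called. Death is an LTPFS event. A reader might also infer that the LTP rate is inflated; the direction is the reverse, because missed events lower LTP and raise LTPFS.

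Other points on that side also have weight:
- The Imaging Charter may say how persistent tumor is read. It could narrow the gap, and it has not been seen.
- The 9.5-point figure needs no surviving TE failure to be re-ablated or read as progressing in 12 months. Nothing in the documents supports that extreme.
- Late dating of an event matters little to a month-12 estimate, apart from censoring in between.
- Missed scans affect all subjects and are not specific to TE failures.
- TE failures are not hidden, since they are the complement of the primary endpoint. The only formal test is on TE.

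The gap nevertheless remains. Re-ablation is optional and is worded for tumors that recur. Other treatment of a residual tumor is not made an event. The Full Analysis Set in SAP Section 6 requires a completed procedure, not TE, so it does not remove these subjects, although the exact LTPFS denominator is open. The charter can settle how scans are read, but the analysis population, event date and censoring belong in the SAP.

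**Conclusion.** The concern holds in this form: a TE failure can, but need not, count as free of LTP and be censored event-free in LTPFS. This follows from three stated rules taken together: the 30-day baseline, the unrestricted set of target tumors, and censoring at last contact. The LTPFS overstatement is 0 to 9.5 points at the planned 90% TE and 0 to 12.4 points at 126/145, assuming 5% deaths among the failures and one target tumor per subject. Where in that range it falls depends on the share of failures never called an event, which the documents do not give; zero is possible. PFS is open to the same effect through its local component. No hypothesis test or sample size depends on LTP, LTPFS or PFS, and the primary conclusion is untouched. The issue is moderate.

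**What to change.** In SAP 8.8.2 and Protocol 4.3:

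1. Report LTP among target tumors with centrally read TE at Visit 3. Show TE failures in a separate row, including those later re-ablated.
2. For LTPFS and the local component of PFS, count a centrally read TE failure as a local failure event dated at the Visit 3 CT. Amend the LTPFS definition to say so, because it would then be wider than LTP or death. Give the present definition as a sensitivity analysis.
3. Align both changes with the re-ablation rule, so that a re-ablated TE failure is one event with one date and appears in the failure row of the LTP table. Align them also with the Imaging Charter's reading rules. State how target tumors without a readable Visit 3 CT are handled.

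The cost is SAP and protocol wording and one derived flag from data that central review already reads. No new assessment is needed. The downside is a somewhat less favourable LTPFS and PFS figure.
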